1. To investigate trends in new user (initiators) prescribing patterns in the two years preceding the relevant Commission Decision (January 2012 – January 2014) and in a similar period following the decision (February 2014– December 2015).
2. To investigate switching patterns between products among prevalent users including reasons for changes (e.g., reimbursement or regulatory and clinical guidance).
3. Within Objectives 1 and 2, to examine any changes in utilisation in groups defined by patient's clinical and demographic risk factors for VTE as detailed in the warnings and contraindications in the European Union Summary of Product Characteristics (SmPC).
4. To examine any differences in the incidence rates of VTE between the two periods specified and, in light of the results for Objective 1-3, to investigate any measurable association between the observed changes in CHC use and changes in the VTE incidence rates.

9. Research methods

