We will consider each CHC individually and, additional to the analysis of individual types of combined oral contraceptives, in our analysis, we will group CHC together according to generation (i.e., the second generation containing levonorgestrel/norgestimate and ethinylestradiol, the third generation containing gestodene/desogestrel and ethinylestradiol and the newer generations containing drospirenone and ethinylestradiol).

Analysis

For each calendar year, we provide estimates of the proportion of each oral contraceptive type and the number of switchers (from one type to another or to a different pill strength) overall and stratified by age at initiation of CHC (18-24, 25-29, 30-34, 35-39, 40-44 and 45-49 years).

We will estimate incidence rates of initiating CHC use per 1000 person years at risk including 95% confidence intervals for each calendar year using incident dispensation as the indicator of CHC initiation. Similarly, we will provide estimates of incidence rates of switching per 1000 person years at risk including 95% confidence intervals for each calendar year of the study period.

In order to assess the effects of the review on initiation as well as on switching of treatment (between January 2012- January 2014 and between February 2014- December 2015), we will perform segmented regression analysis, taking the two time periods into account.

For our analyses we will be using SAS version 9.2 or higher.

WP3

Objectives

To obtain the number and proportion of women initiating different types of oral contraceptives in UK between January 2012 to December 2015 and to investigate switching pattern using data from The Health Improvement Network (THIN) primary care database.

Methods

Study population

For the UK drug utilization study, we will make use of anonymised primary care data from when women consult their general practice to obtain oral contraceptives. For each calendar year of the study period (1 January 2012 to 31 December 2015) we will identify women who were between 18 and 49 years and have been registered for at least two years prior with one of the general practices that contributed data to THIN. Individuals with no oral contraceptives prescription prior to study entry (from 2010 onwards) will be followed up until they receive their first oral contraceptive prescription, they become 50 years of age, 31 December 2015, or leave the practice. The new users are defined as women with no prior prescription of CHC in the two years before.

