To investigate switching patterns among prevalent users, individuals will be defined as prevalent users if they had at least one prescription of oral contraceptives between 1 July 2011 and 1 August 2015. Prevalent users will be followed until switch of treatment, six months after last prescription, becoming 50 years of age, December 31st 2015, leave the practice or death, whichever comes first.

Oral contraceptives

We will consider each CHC individually and, additional to the analysis of individual types of combined oral contraceptives, in our analysis, we will group CHC together according to generation (i.e., the second generation containing levonorgestrel/norgestimate and ethinylestradiol, the third generation containing gestodene/desogestrel and ethinylestradiol and the newer generations containing drospirenone and ethinylestradiol).

Analysis

For each calendar year, we provide estimates of the number of initiators of each oral contraceptive type and the number of switchers (from one type to another or to a different dose) overall and stratified by age at initiation of CHC (18-24, 25-29, 30-34, 35-39, 40-44 and 45-49 years), social deprivation (Quintiles of Townsend Deprivation scores), body mass index (BMI) and smoking status.

We will tabulate the estimates of new users by 1000 person years at risk including 95% confidence intervals for each calendar year. Similarly, we will provide estimates of switchers by 1000 person years at risk including 95% confidence intervals for each calendar year of the study period.

In order to assess the effects of the review on initiation as well as on switching of treatment (between January 2012- January 2014 and between February 2014- December 2015), we will perform segmented regression analysis.

For our analyses we will be using Stata version 14 or higher.

WP4

Objectives

To assess changes in the incidence rate of VTE among women using CHCs of reproductive age in the Netherlands between January 2012- January 2014 and February 2014- December 2015 and to investigate any measurable association between these changes and the observed changes in CHC use.

Methods

Study population

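### WP2 and WP3 plan no person-year rates of CHC initiation or switching by risk group, so a change in the level of use among higher-risk women cannot be told apart from a change in the size or recording of the group

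*Protocol*

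**What the plan says.** Section 8, Objective 3, sets out "to examine any changes in utilisation in groups defined by" the clinical and demographic VTE risk factors in the SmPC. It sits within Objectives 1 (initiation) and 2 (switching).

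**UK (Section 9.2, WP3 Analysis).** For each calendar year, "we provide estimates of the number of initiators of each oral contraceptive type and the number of switchers". The strata attached to that sentence are age at initiation, "social deprivation (Quintiles of Townsend Deprivation scores), body mass index (BMI) and smoking status". The rate sentences follow separately: "We will tabulate the estimates of new users by 1000 person years at risk including 95% confidence intervals for each calendar year", and "Similarly, we will provide estimates of switchers by 1000 person years at risk". Neither names a stratum.

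**Denmark (Section 9.2, WP2 Analysis).** By calendar year the plan gives the share of each product and "the number of switchers (from one type to another or to a different pill strength) overall and stratified by age at initiation of CHC". The rate sentence is "We will estimate incidence rates of initiating CHC use per 1000 person years at risk including 95% confidence intervals for each calendar year", with a parallel sentence for switching. Neither names a stratum. Income and education are obtained, but the WP2 analysis does not stratify by them.

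**Netherlands (Section 9.2, WP1 Analysis).** Numbers and proportions are planned, both of new users per product and of switchers, by age and socioeconomic status. There are no person-time rates.

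The segmented regression is not assigned to any risk group in WP1, WP2 or WP3. The Abstract, under data analysis, plans age-standardised initiations for Denmark and the UK.

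**The concern.** Section 7 describes two messages in the Commission Decision: which CHC types carry the lowest VTE risk, and that CHCs are contraindicated in women with one serious or several risk factors. The first bears on which product a woman receives. The second bears on whether a higher-risk woman is started at all, and to see that one needs the level of initiation in the risk group relative to the women who could have started.

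A count has no such denominator. In WP3 it depends on how many eligible women in the stratum are registered with contributing practices. For BMI and smoking it also depends on how often the factor is recorded. A product share describes only the mix among women who did start. A fall in the number of obese or smoking initiators could therefore be reported as an effect of the Decision when the stratum merely shrank. A real fall could equally be hidden by growth or by better recording.

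**Working it through.** The plan states no figure on this point, so there is none to reproduce. The check compares the planned measures and then asks whether a count or a share can stand in for a rate.

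**1. Which measure carries which strata**

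| Package | By risk group | Rate per 1000 person-years |
|---|---|---|
| WP1 | Number and proportion of new users per product and of switchers; age, socioeconomic status | None |
| WP2 | Product share, number of switchers; age | Initiation and switching; no strata named |
| WP3 | Number of initiators per product, number of switchers; age, deprivation, BMI, smoking | Initiation and switching; no strata named |
| WP6 (VTE) | Rate by age, deprivation, BMI, smoking | Strata named explicitly |

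WP6 shows that the protocol does attach these same strata to person-year rates where VTE is the outcome. For utilisation it attaches them to counts.

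**2. Counts against rates.** Since count = rate × person-time, count ratio = rate ratio × denominator ratio. The inputs below are assumptions, because the documents give no person-time by stratum or window.
- Rate unchanged, denominator ratio 0.80 to 1.25: count ratio 1.00 × 0.80 = 0.80 to 1.00 × 1.25 = 1.25.
- Rate down 20%, denominator up 25%: 0.80 × 1.25 = 1.00. The fall is invisible.
- Rate unchanged, recording of BMI or smoking up uniformly from 80% to 88%: 0.88 / 0.80 = 1.10. Every recorded stratum count rises by 10%.

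**3. Shares against rates** (assumed numbers). With 600 of 1000 initiators on a product, the share is 60%. If initiation halves, 300 of 500 is still 60%.

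**4. Whether the unstratified rate can stand in** (assumed numbers). Take 80 000 person-years at lower risk and 20 000 at higher risk, both at 50 per 1000, so the overall rate is 50.0. Let the higher-risk rate fall to 30 and the other rise to 55: (80 000 × 55 + 20 000 × 30) / 100 000 = 50.0. The overall rate does not move.

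**5. Window length.** The windows last 25 and 23 months, so counts summed per window would fall at a constant rate by 1 − 23/25 = 8%. The WP2 and WP3 stratum figures are by calendar year, so this does not affect them as planned. It is a further reason to use rates when results are brought to the two windows.

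**The case against.** The strongest reply is that the limit to unstratified rates is inferred. No sentence confines the rates to the whole cohort, and in WP3 the rate sentence follows directly on the stratified list, so it could be read as referring back to it. Person-time exists in both cohorts, and an analysis plan that is not shown could add the strata. This has some force: nothing in the design prevents stratified rates. But the protocol is not silent at stratum level. It names the measure, and in the UK that measure is a count, whereas WP6 names the strata for its rates.

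A reader might infer that Objective 3 cannot be answered in any of the three countries. The documents do not support that, for three reasons.
- WP1 plans a proportion of switchers by age and socioeconomic status. This is neither a raw count nor a product share, although its denominator is not defined.
- The Abstract's age-standardised initiations for Denmark and the UK require age-specific initiation figures. WP5 and WP6 do not carry this through, but for age the statement that rates are planned only overall would go too far.
- Counts per product within a stratum give the product mix there. A move towards the lower-risk progestogens among higher-risk women is therefore visible, it does not depend on database size, and it is a real part of Objective 3.

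It is also fair to say that the sizes in the working are illustrations. The documents do not show that UK person-time or recording changed.

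**Conclusion.** The point holds for WP2 and WP3 and for the level of use, not for product mix. As written, the outputs by risk group are counts (UK) or product shares and switcher counts (Denmark), and no rate or before-after regression is assigned to a stratum. A change in initiation or switching among higher-risk women then cannot be separated from a change in the stratum's size or recording. The gap is widest for BMI and smoking, which are available only in the UK, where only counts are planned. It is narrower for initiation by age, because of the Abstract.

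The size cannot be derived from the documents. Under the assumed denominator ratios of 0.80 to 1.25, a count could be 20% too low or 25% too high as a measure of change in the rate. The conclusion rests on reading the rate sentences as unstratified, which the wording of WP6 supports but does not prove. It is worth correcting because the data needed are already in the planned cohorts.

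**What to change.** - **WP2 and WP3:** report initiation and switching rates per 1000 person-years with 95% confidence intervals within each stratum and for each of the two windows, using the at-risk cohorts already defined. Compare the windows within strata. Keep the planned counts and shares beside the rates, since they show the product mix.
- **WP3, BMI and smoking:** classify each woman by the last value recorded before the person-time starts, so that recording at the contraceptive visit itself cannot move her between strata. Keep women with no record as a stratum of their own, in numerator and denominator.
- **WP1:** keep the planned proportions. If population counts from the Central Bureau of Statistics are used as a denominator, label the result as initiations per female population. Those counts include current CHC users, who cannot be new users under the two-year rule, so it would not be a rate among women at risk of new use and would not match WP2 and WP3.

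No new data source is needed. The cost is additional tables and wider intervals in small strata.

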Using data retrieved from electronic health records (see below: Data sources) from three European Union member states, i.e. the Netherlands, Denmark, and United Kingdom, we will address the study objectives in

1. A drug utilization study into prescribing patterns including new use of CHCs and calendar-period specific changes in switching of CHCs
2. A cohort study for incidences of VTE

Population, Variables and Data sources:

For the Dutch drug utilization study and cohort study, we will make use of de-identified data obtained through The Dutch Foundation for Pharmaceutical Statistics (SFK), which gathers its data from >95% of community pharmacies in the Netherlands (<https://www.sfk.nl/english>). All women between the ages of 18-49 years with at least one prescription of combined oral contraceptive use in the period from January 2012 through December 2015 will be included, i.e., both new users as well as prevalent users. New users are defined as women who do not have a prescription of CHC in the two years before starting. We will also obtain information on prevalent users of CHC and thereby we can assess all individual changes (switches) in CHC. Prevalent users of CHC are defined as women who used at least one cycle of CHC. Age at initiation and 4 digit postcodes is also available in the SFK database which allows further characterization of CHC users by age and socioeconomic status. The latter information will be retrieved by using information from the Central Bureau of Statistics (CBS), the Netherlands, which keeps record of socioeconomic status by use of 4-digit postcodes. Although SFK does not indicate if women had venous thrombotic disease for which they need to receive anticoagulant treatment, it can be approximated by the first dose of oral anticoagulant (direct oral anticoagulant (DOAC)) or duration of anticoagulant (vitamin K antagonist), which is specific for VTE.

For the Danish drug utilization and cohort study, data will be linked from the following databases: The Danish Civil Registration System (contains data on age, sex, vital status and migration), the Danish National Prescription Registry (outpatient dispensations of CHC and other

medications), and data on income and education at Statistics Denmark. Women between the ages 18-49 years in the period January 2012- December 2015 will be included, i.e. both new and prevalent users.

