Medication use in the SFK database will be used to approximate the occurrence of VTE by using the first dose of oral anticoagulant, which, in case of DOAC use is specific for VTE or the duration of treatment with Vitamin K antagonists. Incidence of VTE is calculated by following the new users of CHC within each calendar window until they experience a VTE, or up to one year.

We will calculate the incidence among the new users of oral contraceptives in general and per type of oral contraceptive (different types and grouped by generation (second, third and newer generations)).

Analysis

We will tabulate the estimates of the annual incidence of VTE including 95% confidence intervals for each calendar window of the study period.

From segmented regression analysis (WP1), we will obtain information on a potential change in the proportion of initiators of each generation of CHC between January 2012-January 2014 and February 2014- December 2015. Since we have information about the prescription patterns among new users, we can assess whether the changes observed in the proportions of each generation is associated with changes in the incidence rate of VTE in women initiating oral contraceptive use.

Furthermore, we can study the changes in the incidence of VTE within users of different types (and generations) of oral contraceptives. A change in this incidence over time, may indicate that certain preparations are prescribed to low/high risk individuals.

Because we have information about the age and socioeconomic status (risk factors of VTE) of these women, we can stratify analyses on these factors.

For our analysis we will use SPSS for Windows, release 23.0.

WP5

Objectives

To assess changes in the incidence rates of VTE among women of reproductive age overall and by CHC-initiation/switching in Denmark between January 2012-January 2014 and February 2014-December 2015.

Study population

For each calendar year of the study period (1 January 2012 to 31 December 2015) we will identify women who were between 18 and 49 years old. Individuals with no previous record of VTE prior to study entry (from 2002 onwards) will be followed until they are recorded with a VTE, become 50 years of age, 31st of December 2015 or they migrate.

Analysis

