9.5 Limitations of the research methods

Women in the SFK who receive an anticoagulant treatment (DOAC or VKA) are women who survived a thrombosis. Women who died (with a worse prognosis) will not have a treatment prescription and are therefore not identified as cases in this study.

Because we are relying on the anticoagulant treatment as a proxy for women having a VTE, the cases are not confirmed cases, since the real diagnostic criteria for Deep vein Thrombosis (Doppler ultrasonography) and Pulmonary Embolism (ventilation perfusion lung scan, spiral computed tomography, or angiogram) is not assessed.

In Denmark all executed prescriptions are registered in the Danish National Prescription Registry. Combined oral contraceptives are prescription medications and the registration is an automated process, so the data validity is considered high. Regarding VTE occurrence data is obtained from the National Registry of Patients. This registry is automatically updated with all diagnosis codes from Danish Hospital contacts, so as for the Netherlands VTEs that might miss in this project are those with fatal disease that do not attend hospital.

10. Protection of human subjects

No ethical approval is needed.

11. Plans for disseminating and communicating study results

Results from WP1-6 will be combined for the final report for the EMA and in the manuscript for submission for publication in an academic journal.

The abstract of the paper can be submitted for conferences.

12. References

1. Value of the ventilation/perfusion scan in acute pulmonary embolism. Results of the prospective investigation of pulmonary embolism diagnosis (PIOPED). The PIOPED Investigators. JAMA. 1990;263(20):2753-9.

3. [name] A, Helmerhorst FM, Vandenbroucke JP, Doggen CJ, Rosendaal FR. The venous thrombotic risk of oral contraceptives, effects of oestrogen dose and progestogen type: results of the MEGA case-control study. *BMJ*. 2009;339:b2921.

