5.1 Does the protocol describe how the study exposure is defined and measured? (e.g. operational details for defining and categorising exposure, measurement of dose and duration of drug exposure)				9.2 (analysis per WP)
5.2 Does the protocol address the validity of the exposure measurement? (e.g. precision, accuracy, use of validation sub-study)				
5.3 Is exposure classified according to time windows? (e.g. current user, former user, non-use)				Page 9 (population)
5.4 Is exposure classified based on biological mechanism of action and taking into account the pharmacokinetics and pharmacodynamics of the drug?				9.2

Comments:

Ad 5.2 exposure is registered in existing databases

Section 6: Outcome definition and measurement	Yes	No	N/A	Section Number
6.1 Does the protocol specify the primary and secondary (if applicable) outcome(s) to be investigated?				9.2 (specified per WP)
6.2 Does the protocol describe how the outcomes are defined and measured?				9.2 (analysis per WP)
6.3 Does the protocol address the validity of outcome measurement? (e.g. precision, accuracy, sensitivity, specificity, positive predictive value, prospective or retrospective ascertainment, use of validation sub-study)				
6.4 Does the protocol describe specific endpoints relevant for Health Technology Assessment? (e.g. HRQoL, QALYs, DALYS, health care services utilisation, burden of disease, disease management)				

Comments:

--

Section 7: Bias	Yes	No	N/A	Section Number
7.1 Does the protocol describe how confounding will be addressed in the study?				9.2 (stratification)
7.1.1. Does the protocol address confounding by indication if applicable?				

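### The Dutch VTE proxy uses a different case rule for each anticoagulant class, so a change in class mix between the two windows may look like a change in VTE unless both rules capture VTE equally

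*Protocol*

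**What the plan says.** The SFK pharmacy data hold no diagnosis, so a Dutch VTE case is approximated from anticoagulant dispensing. The rule appears in three places. Section 9.2, WP4 (Study population) uses the "first dose of oral anticoagulant, which, in case of DOAC use is specific for VTE or the duration of treatment with Vitamin K antagonists". The Abstract and section 9.2, WP1 use the "first dose of oral anticoagulant (direct oral anticoagulant (DOAC)) or duration of anticoagulant (vitamin K antagonist), which is specific for VTE". In each, a DOAC user qualifies on one kind of evidence and a vitamin K antagonist (VKA) user on another.

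WP4 aims to assess change in VTE incidence "in the Netherlands between January 2012- January 2014 and February 2014- December 2015" and to relate it to change in CHC use. Incidence comes from "following the new users of CHC within each calendar window until they experience a VTE, or up to one year". The analysis is to "tabulate the estimates of the annual incidence of VTE including 95% confidence intervals for each calendar window". Results are broken down by CHC type and generation, with stratification by age and socioeconomic status. No breakdown by anticoagulant class is planned.

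Section 9.5 acknowledges the proxy: "Because we are relying on the anticoagulant treatment as a proxy for women having a VTE, the cases are not confirmed cases". It adds that fatal cases are missed. It does not say that the two rules may differ in accuracy, or that the anticoagulant mix may differ between windows. In the ENCePP checklist, item 6.3 ("Does the protocol address the validity of outcome measurement") and item 12.1.2 (impact of information bias) are marked not applicable.

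**The concern.** A before/after comparison of incidence needs an outcome measure whose capture is stable over time. Misclassification that is the same in both windows largely cancels from a rate ratio. Misclassification that depends on drug class does not cancel if the class mix moves.

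Here the outcome rule itself depends on drug class. A first-dose rule and a duration rule will in general differ both in the true cases they miss and in the non-VTE treatment they admit. The WP4 contrast is meant to feed a report on whether the recommendation affected VTE incidence. A shift in anticoagulant prescribing could mask a real fall or create an apparent one, and nothing in the planned tables would reveal it.

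**Working it through.** The protocol states no Dutch case count, class share, sensitivity or positive predictive value (PPV), so there is no plan figure to reproduce. The check is algebraic, with true VTE held constant.

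**Definitions.** Let d1 and d2 be the shares of true, treated VTE cases that receive a DOAC in windows 1 and 2. Let cD and cV be measured cases per true case under each rule, where c = sensitivity / PPV, assumed constant over time within a class. Then

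measured ratio = [d2·cD + (1 − d2)·cV] / [d1·cD + (1 − d1)·cV].

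**Equal capture.** If cV = cD, the ratio is 1.000 for every d1 and d2. A shift in mix does no harm in that case.

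**Unequal capture.** Put k = cV/cD. For d1 = 5%, d2 = 30%, k = 0.8: (0.30 + 0.70 × 0.8) / (0.05 + 0.95 × 0.8) = 0.86/0.81 = 1.062. All shares and k values below are assumptions.

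| DOAC share | k = 0.95 | k = 0.9 | k = 0.8 | k = 0.7 | k = 1.1 |
|---|---|---|---|---|---|
| 5% to 30% | 1.013 | 1.028 | 1.062 | 1.105 | 0.977 |
| 0% to 50% | 1.026 | 1.056 | 1.125 | 1.214 | 0.955 |

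**Dependence on the accuracy assumptions.** Suppose the DOAC rule misses no case and the VKA rule admits no false case.
- With the share moving from 5% to 40%, VKA sensitivity 0.85 and DOAC PPV 0.90: (0.40/0.90 + 0.60 × 0.85) / (0.05/0.90 + 0.95 × 0.85) = 0.954/0.863 = 1.106.
- With the share moving from 10% to 60%, sensitivity 0.85 and DOAC PPV 0.80: (0.75 + 0.34) / (0.125 + 0.765) = 1.09/0.89 = 1.225.

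Those settings put every miss in one class and every false positive in the other. If the VKA rule also admits false cases, the 1.106 falls to 1.039 at VKA PPV 0.85, to 1.016 at 0.80 and to 0.993 at 0.75. The sign of the artefact is therefore not determined.

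**Size of the effect sought.** The risk table in the Abstract gives 5-7 per 10,000 per year for the lower-risk CHC group and 9-12 for drospirenone, gestodene or desogestrel; the midpoints are 6 and 10.5. The shifts are assumed.
- Higher-risk share 50% to 40%: (0.4 × 10.5 + 0.6 × 6) / (0.5 × 10.5 + 0.5 × 6) = 7.80/8.25 = 0.945 (0.918 to 0.975 over the corners of the stated ranges).
- Higher-risk share 30% to 10%: (0.1 × 10.5 + 0.9 × 6) / (0.3 × 10.5 + 0.7 × 6) = 6.45/7.35 = 0.878.

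**Together.** A true ratio of 7.80/8.25 multiplied by an artefact of 0.86/0.81 gives 1.004, so the fall would be hidden. With k = 1.1 and the same 5% to 30% shift, the artefact is 1.07/1.095 and the product is 0.924, so the fall would be overstated.

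**The case against.** The strongest reply is that first dose need not mean one dispensing. It can be read as the starting dose level, which would make the two rules class-appropriate markers of indication, chosen because different evidence identifies VTE for each class. On that reading DOAC courses started at another dose level are excluded, and the specificity claim is easier to defend. This stands as a fair reading, and it means nobody can assume that the DOAC rule is the looser one. It does not make the two rules equal in capture, and the wording leaves the reading open.

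A reader might also infer that any shift between classes must change measured incidence, or that measured VTE will rise and conceal a true fall. The documents support neither. Equal capture gives exactly 1.000, the ratio falls below 1 if the VKA rule captures more, and no document shows that a class shift took place. This is an uncontrolled risk to the comparison and not a demonstrated bias.

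It can be said, too, that the VKA duration threshold may sit in an analysis plan that is not shown. Its absence is not counted here. The point is the class-dependent definition that the protocol itself fixes.

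Finally, making a common minimum duration the primary definition would have a real price. It discards dose information and needs dispensings after the event, so DOAC cases late in the second window could become unascertainable if the data stop in December 2015. That objection stands and shapes the fix.

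**Conclusion.** The point holds in conditional form. The protocol defines Dutch VTE by class-specific rules, compares incidence across calendar windows, and plans nothing that would detect or remove an effect of changing anticoagulant mix. A change in mix may alter measured incidence with no change in VTE unless both rules capture equally.

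Direction and size are unknown. In the scenarios shown, the artefact ratio runs from 0.955 to 1.225, with 1.000 under equal capture. The effect sought is about 0.88 to 0.95 at mid-range risks. Both ranges rest on assumed shifts; only the CHC risks come from the protocol. The comparison shows that the artefact could match the effect, not that it will.

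The reach is limited. Denmark and the United Kingdom use recorded diagnoses, and VTE changes are reported separately by country, so only the Dutch estimate is exposed. This is a cheap improvement.

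**What to change.** Keep the planned case definition as primary and add the following to WP4.

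1. Tabulate DOAC-identified and VKA-identified cases, and the incidence of each, by window, with the DOAC share of identified cases. If capture within each class is constant over time, an unchanged share rules out this artefact. A changed share shows that step 2 is needed to interpret the contrast.
2. Add a sensitivity analysis applying one common rule to both classes, for example the same minimum duration, with a switch between classes counted as one episode. Restrict it to initiators with enough data after the event to assess the rule. A common rule makes the classes more comparable but does not guarantee equal capture, so read it alongside step 1.
3. State whether first dose means first dispensing or starting dose level.
4. In section 9.5, present the claim that the rule is specific to VTE as an assumption, and note that accuracy may differ by class and the mix by window.

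The cost is a little more analysis on dispensings of the kind WP4 already uses. Some early-stopping and late-window cases are lost, but only in the sensitivity analysis.
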